## **7.3 Disposition of Subjects**

### **7.3.1 Study Information**

Analysis Set: All Subjects Who Signed the Informed Consent Form  
Analysis Variable(s): Date First Subject Signed Informed Consent Form  
Date Last Subject Completed Study Drug Administration  
MedDRA Version  
SAS Version Used for Creating the Datasets  
Analysis Method(s): The following analysis will be performed for the above analysis variables.  
(1) Display of analysis variables

### **7.3.2 Subject Eligibility**

Analysis Set: All Subjects Who Signed the Informed Consent Form  
Analysis Variable(s): Randomization [Eligible for Randomization, Not Eligible for Randomization]  
Primary Reason for Subject Not Being Eligible [Adverse Event, Death, Lost to Follow-up, Protocol Deviation, Sufficient Subject, Screening Failure, Study Termination by Sponsor, Voluntary Withdrawal, Other]  
Analysis Method(s): The following analysis will be performed for the above analysis variables.  
When calculating percentages for the primary reasons for subject not eligible for randomization, the total number of subjects who were not eligible for randomization will be used as the denominator.  
(1) Frequency distributions

### **7.3.3 Disposition of Subjects**

Analysis Set: All Subjects Who Were Eligible for Randomization  
Analysis Variable(s): Study Completion Status [Completed All Planned Study Visits, Did Not Complete All Planned Study Visits]  
Reason for Discontinuation of Study Visits [Adverse Event, Death, Lost to Follow-up, Protocol Deviation, Study Termination by Sponsor, Voluntary Withdrawal, Other]  
Analysis Method(s): The following summaries will be provided by treatment group and by combining the treatment groups. When calculating percentages for the primary reasons for subject who did not complete all planned study visits, the total number of subjects who did not complete all planned study visits will be used as the denominator.  
(1) Frequency distributions

### 7.3.4 Protocol Deviations and Analysis Sets

#### 7.3.4.1 Protocol Deviations

Analysis Set:	All Subjects Who Were Eligible for Randomization
Analysis Variable(s):	Protocol Deviations [Deviations of Protocol Entry Criteria, Deviations Concerning Excluded Medication or Therapy, Noncompliance with Protocol, Deviations Related to Treatment Procedure or Dose, Deviations of Discontinuation Criteria, Major GCP Violations]
Analysis Method(s):	
The following summaries will be provided by treatment group and by combining the treatment groups.
 
The number of subjects with protocol deviations will be calculated and the details of deviations will be shown after classifying the contents of deviations into the above categories. A subject who has several categories will be counted once in each appropriate category.
 
(1) Frequency distributions

#### 7.3.4.2 Analysis Sets

Analysis Set:	All Subjects Who Were Eligible for Randomization
Analysis Variable(s):	Handling of Subjects in Analysis Sets [Categories are based on the specifications in the List of Subject Evaluability Assignments]
	Inclusion/Exclusion of Analysis Set
	Safety Analysis Set [Included]
	PK Analysis Set [Included]
Analysis Method(s):	
The following summaries will be provided by treatment group for (1), and by treatment group and by combining the treatment groups for (2).
 
For (1), a subject who has several categories will be counted once in each appropriate category.
 
(1) Frequency distributions for handling of cases in each analysis set
 
(2) Frequency distributions for number of cases included in each analysis set

### 7.4 Demographic and Other Baseline Characteristics

Analysis Set:	Safety Analysis Set
	PK Analysis Set

Analysis Variable(s):	Age (years) Height (cm) Weight (kg) (prior to administration in Period 1) BMI (kg/m  ) (prior to administration in Period 1) Smoking Classification Alcohol Classification Caffeine Classification	[The subject has never smoked, The subject is a current smoker, The subject is an ex-smoker] [Everyday, 2 to 3 Days a Week, 2 to 3 Days a Month, Never] [Yes, No]
Analysis Method(s):	The following summaries will be provided by treatment group and by combining the treatment groups. In case an add-on subject study was conducted, the analysis will be performed for the study which was conducted with the originally planned number of subjects and for each add-on study. (1) Frequency distributions for categorical variables and descriptive statistics for continuous variables	

## **7.5 Medical History and Concurrent Medical Conditions**

Not applicable in this study.

## **7.6 Medication History and Concomitant Medications**

Not applicable in this study.

## **7.7 Study Drug Exposure and Compliance**

Not applicable in this study.

## **7.8 Efficacy Analysis**

### **7.8.1 Primary Efficacy Endpoint**

Not applicable in this study.

### **7.8.2 Secondary Efficacy Endpoint**

Not applicable in this study.

### 7.8.3 Additional Efficacy Endpoint

Not applicable in this study.

### 7.8.4 Statistical/Analytical Issues

#### 7.8.4.1 Adjustments for Covariates

Not applied in this study.

#### 7.8.4.2 Handling of Dropouts or Missing Data

Missing test results or data determined to be non-evaluable according to this Statistical Analysis Plan will not be used for hypothesis testing and estimations.

Values below the lower limit of quantification in drug concentrations and laboratory test values will be treated as zero, and values above the upper limit of quantification in laboratory test values will be treated as the upper limit of quantification.

#### 7.8.4.3 Multicenter Studies

Not applied in this study.

#### 7.8.4.4 Multiple Comparison/Multiplicity

Not applied in this study.

#### 7.8.4.5 Use of an "Efficacy Subset" of Subjects

Not applied in this study.

#### 7.8.4.6 Active-Control Studies Intended to Show Equivalence or Non-Inferiority

The bioequivalence of the formulations (TAK-536 commercial formulation and TAK-536 pediatric formulation) will be evaluated according to the criteria set forth in the Guideline for Bioequivalence Studies of Generic Products [1]. The formulations will be considered bioequivalent if the 90% CIs (two-sided) of the differences in the means of the natural log-transformed AUC48 and Cmax of TAK-536 between the TAK-536 commercial formulation and the TAK-536 pediatric formulation fall within the range of  $\ln(0.80) - \ln(1.25)$ .

When the 90% CIs do not fall within the range of  $\ln(0.80) - \ln(1.25)$  with an add-on subject study, the formulations will be considered bioequivalent if the differences in the means of the natural log-transformed parameters AUC48 and Cmax of TAK-536 between the TAK-536 commercial formulation and the TAK-536 pediatric formulation fall within the range of

$\ln(0.90) - \ln(1.11)$ , and the results of the dissolution test meet the conditions specified in the Guideline for Bioequivalence Studies of Generic Products. However, the above provision will be applicable only if the combined number of subjects in this study and an add-on subject study is 30 subjects or greater.

*7.8.4.7 Examination of Subgroups*

Not applied in this study.

## 7.9 Pharmacokinetic/Pharmacodynamic Analysis

### 7.9.1 Pharmacokinetic Analysis

### 7.9.1.1 Plasma Concentrations

### Analysis Set: PK Analysis Set

Analysis Variable(s): Plasma Concentrations of TAK-536

Visit: Predose, 0.5, 1, 1.5, 2, 2.5, 3, 3.5, 4, 5, 6, 8, 12, 16, 24, and 48 Hours Postdose

Analysis Method(s): The following analysis will be performed for the above analysis variables.

Variables:

- (1) Descriptive statistics will be provided for each formulation by visit.
- (2) Mean and standard deviation will be plotted simultaneously for both formulations (vertical axis: normal scale).
- (3) Mean will be plotted simultaneously for both formulations (vertical axis: common logarithmic scale).

### 7.9.1.2 Pharmacokinetic Parameters

Analysis Set: PK Analysis Set

Analysis Variable(s): Pharmacokinetic Parameters of TAK-536

AUC48	AUClast	Cmax
AUCinf	MRTlast,ev	tmax
Lambda z	t1/2z	CL/F
Vz/F	MRTinf ev	

Analysis Method(s): The following analysis will be performed for the above analysis variables by formulation.

Variables by formulation:

(1) Summary of Pharmacokinetic Parameters

For AUC48, AUClast, Cmax, and AUCinf, descriptive statistics, geometric mean, and CV will be provided.

For Tmax, descriptive statistics will be provided.

For all other variables, descriptive statistics and CV will be provided.

### 7.9.1.3 Treatment Ratio in Pharmacokinetic Parameters

Analysis Set: PK Analysis Set

Analysis Set: Analysis Set  
Analysis Variable(s): Treatment Ratio of (TAK-536 commercial formulation/TAK-536 pediatric formulation) in AUC48 and Cmax of TAK-536

Analysis Method(s): The following analysis will be performed for the above analysis variables

(1) Descriptive statistics will be provided for treatment ratio of pharmacokinetic parameters.

#### *7.9.1.4 Assessment of Bioequivalence*

##### Primary Endpoints

Analysis Set: PK Analysis Set  
Analysis Variable(s): Pharmacokinetic Parameters of TAK-536  
                          AUC48          Cmax  
Analysis Method(s): The following analysis will be performed for the above analysis variables. In case an add-on subject study was conducted, the analysis will be performed for the study which was conducted with the originally planned number of subjects and for each add-on study.

(1) The difference in the least square means between formulations (TAK-536 pediatric formulation – TAK-536 commercial formulation) and the two-sided 90% confidence interval will be provided using a crossover ANOVA model. The ANOVA model will include log-transformed (natural log) analysis variables as dependent variable, and formulation, treatment group, and period as independent variables.

##### Secondary Endpoints

Analysis Set: PK Analysis Set  
Analysis Variable(s): Pharmacokinetic Parameters of TAK-536  
                          AUClast          AUCinf          MRTinf,ev  
                          Lambda z          tmax  
Analysis Method(s): The following analysis will be performed for the above analysis variables.

(1) The difference in the least square means between formulations (TAK-536 pediatric formulation - TAK-536 commercial formulation) and the two-sided 90% confidence interval will be provided using a crossover ANOVA model. The ANOVA model will include log-transformed (natural log) analysis variables other than tmax as dependent variable, and formulation, treatment group, and period as independent variables.

(2) The difference in the least square means between formulations (TAK-536 pediatric formulation – TAK-536 commercial formulation) and the two-sided 90% confidence interval will be provided using a crossover ANOVA model. The ANOVA model will include non-natural log-transformed tmax as dependent variable, and formulation, treatment group, and period as independent variables.

#### *7.9.1.5 Individual Plasma Concentrations*

Analysis Set: All Subjects Who Entered the Treatment Period  
Analysis Variable(s): Plasma Concentrations of TAK-536

Visit: Predose, 0.5, 1, 1.5, 2, 2.5, 3, 3.5, 4, 5, 6, 8, 12, 16, 24, and 48 Hours  
Postdose

Analysis Method(s): The following analysis will be performed for the above analysis variables.  
(1) Individual plasma concentrations will be plotted simultaneously for both formulations (vertical axis: normal scale).

#### *7.9.1.6 Subject Data Listings for Pharmacokinetic Parameters*

Analysis Set: All Subjects Who Entered the Treatment Period

Analysis Variable(s): Pharmacokinetic Parameters of TAK-536

AUC48	AUClast	MRTlast,ev
Cmax	tmax	AUCinf
Lambda z		
Measuring points of estimating Lambda z (start point, end point, and number of points) and adjusted R-squared contribution rate		
t1/2z	CL/F	Vz/F
MRTinf,ev		

#### *7.9.1.7 Subject Data Listings for Treatment Ratio in Pharmacokinetic Parameters*

Analysis Set: All Subjects Who Entered the Treatment Period

Analysis Variable(s): Treatment Ratio of (TAK-536 commercial formulation/TAK-536 pediatric formulation) in AUC48 and Cmax of TAK-536

Analysis Method(s): Subject data listings including the following variables will be displayed.  
(1) Subject ID, subject number, and treatment group

### **7.9.2 Pharmacodynamic Analysis**

Not applicable in this study.

### **7.10 Other Outcomes**

Not applicable in this study.

## 7.11 Safety Analysis

### 7.11.1 Adverse Events

#### 7.11.1.1 Overview of Treatment-Emergent Adverse Events

Analysis Set: Safety Analysis Set  
Analysis Variable(s): TEAE  
Categories: Relationship to Study Drug [Related, Not Related]  
Intensity [Mild, Moderate, Severe]  
Analysis Method(s): The following analysis will be performed for the above analysis variables by formulation.

- (1) Overview of TEAE
  - 1) All TEAEs (number of events, number and percentage of subjects)
  - 2) Relationship of TEAEs to study drug (number of events, number and percentage of subjects)
  - 3) Intensity of TEAEs (number of events, number and percentage of subjects)
  - 4) TEAEs leading to study drug discontinuation (number of events, number and percentage of subjects)
  - 5) Serious TEAEs (number of events, number and percentage of subjects)
  - 6) Relationship of serious TEAEs to study drug (number of events, number and percentage of subjects)
  - 7) Serious TEAEs leading to study drug discontinuation (number of events, number and percentage of subjects)
  - 8) TEAEs resulting in death (number of events, number and percentage of subjects)

TEAEs will be counted according to the rules below. When calculating percentages for TEAE, the number of subjects who were treated by that formulation in the safety analysis set will be used as the denominator.

[Number of subjects with TEAEs]

- In case of “frequency distributions by relationship to study drug”  
A subject with occurrences of TEAE in both categories (i.e., Related and Not Related) will be counted once in the Related category.
- In case of “frequency distributions by intensity”  
A subject with multiple occurrences of TEAE will be counted once for the TEAE with the maximum intensity.
- In case of distributions other than the above  
A subject with multiple occurrences of TEAE will be counted only once.

[Number of events]

For each summary, the total number of events will be calculated.

#### *7.11.1.2 Displays of Treatment-Emergent Adverse events*

Analysis Set: Safety Analysis Set  
Analysis Variable(s): TEAE  
Categories: Intensity [Mild, Moderate, Severe]  
Analysis Method(s): The following analysis will be performed for the above analysis variables by formulation.  
TEAEs will be coded using the MedDRA and will be summarized using SOC and PT. SOC will be sorted alphabetically and PT will be sorted in decreasing frequency for tables provided by SOC and PT. SOC and PT will be sorted in decreasing frequency for tables provided by SOC only or PT only.  
(1) All TEAEs by SOC and PT  
(2) All TEAEs by SOC  
(3) All TEAEs by PT  
(4) Drug-Related TEAEs by SOC and PT  
(5) Intensity of All TEAEs by SOC and PT  
(6) Intensity of Drug-Related TEAEs by SOC and PT  
(7) TEAEs Leading to Study Drug Discontinuation by SOC and PT  
(8) Serious TEAEs by SOC and PT  
The method of counting events when conducting each frequency distribution will be as follows:  
[Number of subjects with TEAEs]

- In case of “frequency distributions by SOC and PT, by SOC only, or PT only”  
A subject with multiple occurrences of TEAE within a SOC will be counted only once in that SOC. A subject with multiple occurrences of medical history or concurrent medical condition within a PT will be counted only once in that PT. Also, when calculating percentages for TEAE, the number of subjects who were treated by that formulation in the safety analysis set will be used as the denominator.
- In case of “frequency distributions by SOC and PT”  
A subject with multiple occurrences of TEAE within a SOC or a PT will be counted only once for the TEAE with the maximum intensity. Also, when calculating percentages for TEAE, the number of subjects who were treated by that formulation in the safety analysis set will be used as the denominator.

#### *7.11.1.3 Displays of Pretreatment Events*

Analysis Set: All Subjects Who Signed the Informed Consent Form  
Analysis Variable(s): PTE  
Analysis Method(s): The following analysis will be performed for the above analysis variables.  
PTEs will be coded using the MedDRA and will be summarized

using SOC and PT, where SOC will be sorted alphabetically and PT will be sorted in decreasing frequency.

- (1) All PTEs by SOC and PT
- (2) Serious PTEs by SOC and PT

The method of counting events when conducting each frequency distribution will be as follows:

[Number of subjects with PTEs]

- A subject with multiple occurrences of PTE within a SOC will be counted only once in that SOC. A subject with multiple occurrences of medical history or concurrent medical condition within a PT will be counted only once in that PT.

## **7.11.2 Clinical Laboratory Evaluations**

### *7.11.2.1 Hematology and Serum Chemistry*

Analysis Set:	Safety Analysis Set		
Analysis Variable(s):	Hematology		
	RBC	WBC	Hemoglobin
	Hematocrit	Platelets	
	WBC Differentials (Neutrophil, Basophil, Eosinophil, Lymphocyte, and Monocyte)		
	Serum Chemistry		
	ALT	AST	
	Alkaline Phosphatase		
	GGT	Total Bilirubin	Total Protein
	Albumin	Creatinine	Urea Nitrogen
	Potassium	Sodium	Chloride
	Calcium	Inorganic Phosphorus	Total Cholesterol
	Fasting	Urine Acid	LDH
	Triglycerides		
	Creatine Kinase		Fasting Glucose
Categories:	Results of determination based on reference values [Below lower limit of reference value, Within the range of reference value, Over upper limit of reference value]		
Visit:	Predose, 24 and 48 Hours Postdose, Follow-up Examination (Day 6)		
Analysis Method(s):	The following analysis will be performed for the above analysis variables by formulation.		
	

(1) Descriptive statistics for observed values for each visit and changes (each visit after administration-predose) will be provided.

(2) Case Plots

(3) A shift table for each visit before and after administration will be provided for the results of determination based on the

		

reference values.

#### **7.11.2.2 Urinalysis**

Analysis Set:	Safety Analysis Set
Analysis Variable(s):	Specific Gravity pH Glucose Protein Blood Ketone Body Bilirubin Urobilinogen
Categories:	Results of determination based on reference values [Below lower limit of reference value, Within the range of reference value, Over upper limit of reference value]
Visit:	Predose, 24 and 48 Hours Postdose, Follow-up Examination (Day 6)
Analysis Method(s):	For specific gravity, summaries (1) to (3) will be provided by formulation. For each variable other than specific gravity, summaries (3) will be provided. (1) Descriptive statistics for observed values for each visit and changes (each visit after administration-predose) will be provided. (2) Case Plots (3) A shift table for each visit before and after administration will be provided for the results of determination based on the reference values.

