9.1.8 Procedures for Clinical Laboratory Samples

All samples will be collected in accordance with acceptable laboratory procedures. Laboratory samples will be taken following a minimum 8 hour overnight fast on the days stipulated in the Schedule of Study Procedures ([Appendix A](#)).

[Table 9.a](#) lists the tests that will be obtained for each laboratory specimen.

Table 9.a Clinical Laboratory Tests

Hematology	Serum Chemistry	Urinalysis
Red blood cells (RBC)	ALT	pH
White blood cells (WBC)	AST	Specific gravity
with differential (neutrophils, basophils, eosinophils, lymphocytes, monocytes)	ALP	Qualitative tests for glucose, protein, occult blood, ketone body, bilirubin, and urobilinogen
Hemoglobin	GGT	
Hematocrit	Total bilirubin	
Platelets	Total protein	
	Albumin	
	Creatinine	
	BUN	
	Potassium	
	Sodium	
	Chloride	
	Calcium	
	Inorganic phosphorus	
	Total cholesterol	
	Fasting triglyceride	
	Uric acid	
	LDH	
	Creatine kinase	
	Fasting glucose	

Only for eligibility assessment:

Serum (immunology tests)	Urine (urine drug tests)
HBsAg, HCV antibody, HIV antigen/antibody, serum test for syphilis	phencyclidine, benzodiazepines, cocaine, antihypnotic agents, cannabinoids, opioids, barbiturates, and tricyclic antidepressants

Note: The investigator or sub-investigator will report the results of immunology and urine drug tests directly to subjects. The sponsor will confirm the overall test results ("Positive" or "All negative"), rather than detailed results, for subjects (including reserve subjects) to be administered the study drug.

The local laboratory will perform laboratory tests for hematology, serum chemistry, and urinalysis. The results of laboratory tests will be returned to the investigator or sub-investigator, who is responsible for reviewing and filing these results.

If subjects experience ALT or AST $>3\times$ ULN, follow-up laboratory tests (at a minimum, ALP, ALT, AST, total bilirubin, GGT, and INR) should be performed within a maximum of 7 days and preferably within 48 to 72 hours after the abnormality was noted (Refer to Section 7.5 and Section 10.2.3 for the appropriate guidance on reporting abnormal liver function tests).

The investigator will maintain a copy of the reference ranges for the laboratory used.

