13.1.4 Safety Analysis

The following statistical analyses will be performed on the safety analysis set.

1. Adverse events (treatment emergent adverse events)

A treatment emergent adverse event (TEAE) is defined as an event whose date of onset occurs on or after the start of study drug.

TEAEs will be coded using the MedDRA dictionary. The frequency distribution will be provided using the system organ class and the preferred term for each treatment as follows:

- All TEAEs
- Drug-related TEAEs
- Intensity of TEAEs
- Intensity of drug-related TEAEs
- TEAEs leading to study drug discontinuation
- Serious TEAEs

2. Laboratory test results, resting 12-lead ECGs, and vital signs (sitting blood pressure, sitting pulse [beats per minute], and body temperature), weight

For continuous variables, the observed values and the changes from baseline will be summarized by treatment for each visit using descriptive statistics. Case plots for the observed values will also be provided for each treatment.

For categorical variables, shift tables showing the number of subjects in each category at baseline and each post-baseline visit will be provided for each treatment.

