#### **7.11.4 12-Lead ECGs**

Analysis Set:	Safety Analysis Set
Analysis Variable(s):	Heart Rate RR Interval PR Interval QRS Interval QT Interval QTcF Interval
	12-Lead ECG Interpretation [Within Normal Limits, Abnormal but not Clinically Significant, Abnormal and Clinically Significant]
Visit:	Predose, 48 Hours Postdose, Follow-up Examination (Day 6)
Analysis Method(s):	For each variable other than 12-lead ECG interpretations, summaries (1) and (2) will be provided by formulation. For 12-lead ECG, summaries (3) will be provided by formulation. (1) Descriptive statistics for observed values for each visit and changes (each visit after administration-predose) will be provided. (2) Case Plots (3) A shift table for each visit before and after administration will be provided.

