### **7.13 Changes in the Statistical Analysis Plan**

The analysis plan described in this Statistical Analysis Plan is the same as the analysis plan described in the protocol.

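### SAP 7.11.2.2 shift tables hide worsening within a reference category for six qualitative urine tests; the section also omits the formulation split and the pH summaries implied by Protocol 13.1.4

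*SAP*

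**What the plan says.** Protocol 9.1.8 (Table 9.a) lists urine pH and specific gravity, and then separately "Qualitative tests for glucose, protein, occult blood, ketone body, bilirubin, and urobilinogen".

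SAP 7.11.2.2 gives one category set for all eight urinalysis variables: "Below lower limit of reference value, Within the range of reference value, Over upper limit of reference value". It defines three outputs: (1) descriptive statistics of observed values and changes, (2) case plots and (3) a shift table. They are allocated in two sentences. The first is "For specific gravity, summaries (1) to (3) will be provided by formulation". The second is "For each variable other than specific gravity, summaries (3) will be provided".

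For categorical safety variables, Protocol 13.1.4 states that "shift tables showing the number of subjects in each category at baseline and each post-baseline visit will be provided for each treatment". For continuous ones it asks for descriptive statistics of values and changes by treatment and visit, together with case plots.

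SAP 7.13 declares no departure: "The analysis plan described in this Statistical Analysis Plan is the same as the analysis plan described in the protocol".

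**The concern.** There are three separate issues in one short section.

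- **Categories (six variables).** A below/within/over scheme suits a numeric analyte with a reference range. For a qualitative test whose reference is negative, the lowest category is empty and every positive grade falls into the highest. The shift table then cannot show worsening in a subject who was already positive at predose, and it cannot tell a new low-grade positive from a new 3+.
- **Formulation split (seven variables).** The split is stated for specific gravity and not for the rest. A programmer working only from that sentence could pool tablet and granules.
- **pH (one variable).** pH stands apart from the qualitative tests in Table 9.a, yet it receives only the shift table.

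The safety of the pediatric formulation is the study's only secondary objective, and urinalysis is a named secondary safety endpoint. For the six qualitative tests, the shift table is the only summary of results that SAP 7.11 specifies.

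**Working it through.** The plan gives no figure to reproduce. The check compares the texts and then counts what the category rule can hide.

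**1. Formulation split, section by section**

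| Place | Split stated? |
|---|---|
| SAP 7.11.2.1, hematology and chemistry | Yes: "The following analysis will be performed for the above analysis variables by formulation" |
| SAP 7.11.2.2, specific gravity | Yes |
| SAP 7.11.2.2, all other variables | No |
| SAP 7.11.3, vital signs and weight | Yes |
| SAP 7.11.4, ECG interpretation shift table | Yes: "For 12-lead ECG, summaries (3) will be provided by formulation" |
| Protocol 13.1.4, categorical shift tables | Yes, for each treatment |

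The ECG section uses the same two-sentence layout and repeats the split in both sentences. The urinalysis section does not. Variables without a stated split: 8 − 1 = 7. Read literally, with the planned 14 subjects dosed in both periods, an unsplit table would hold up to 14 × 2 = 28 subject-periods.

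**2. Worsenings hidden by the categories**

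The grading scale and the cut-off are assumptions, because the documents give neither. With k ordered grades there are C(k,2) possible one-way worsenings. A worsening is hidden when both grades fall in the same category. If w grades count as within reference and the other k − w as over, the number hidden is C(w,2) + C(k − w,2).

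| Assumed grades | Within reference | Possible | Hidden |
|---|---|---|---|
| −, ±, 1+, 2+, 3+ | − | C(5,2) = 10 | C(1,2) + C(4,2) = 0 + 6 = 6 |
| −, ±, 1+, 2+, 3+ | − and ± | C(5,2) = 10 | C(2,2) + C(3,2) = 1 + 3 = 4 |
| −, 1+, 2+, 3+ | − | C(4,2) = 6 | C(1,2) + C(3,2) = 0 + 3 = 3 |

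In every setting, a move from within to over reference is visible. These are counts of possible transitions, not expected numbers of subjects. If the laboratory reports only negative or positive, then k = 2 and w = 1: there is C(2,2) = 1 possible worsening and none is hidden.

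**3. pH**

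SAP 7.11.2.2 gives pH output (3) only. If pH is reported as a number, Protocol 13.1.4 calls for descriptive statistics and case plots as well, which are outputs (1) and (2). The below/within/over categories themselves suit a numeric pH, so the first issue does not apply to it.

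**The case against.** A reader might infer that a urinary change cannot be tied to the pediatric formulation at all. The documents do not support that. Protocol 13.1.4 requires the split, and SAP 7.13 says the two plans agree, so the missing words are most naturally read in from the protocol. Pooling would also count each crossover subject twice in a table meant to count subjects.

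A reader might also infer that worsening goes unseen altogether. Protocol 9.1.8 has laboratory abnormalities judged clinically significant recorded as adverse events. SAP 7.11.1 tabulates treatment-emergent events by formulation, with intensity and relationship to study drug. A clinically significant rise in urine protein or blood would be reported that way.

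The hidden case is narrow too. It mostly needs a subject already over reference at predose, and exclusion criterion 17 removes men whose laboratory values suggest clinically significant disease. In healthy men the likelier event is a new positive from a negative predose result, and that shows as a shift.

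Finally, Protocol 13.1.4 does not define the shift categories, so below/within/over does not contradict it. Asking for grades is an improvement, not a correction of non-compliance.

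All of this stands, and it limits the point. It does not remove it. The adverse-event route captures only changes judged clinically significant, and that judgement is made in an open-label study; a laboratory table is meant to show changes independently of it. Exclusion 17 does not require a negative urinalysis, so predose positives are possible in either period. A general statement that the plans agree shows what was intended but leaves the operative sentence incomplete, although Protocol 13.1 relies on the SAP for the analysis detail.

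**Conclusion.** The point holds as a low-cost improvement to one secondary safety table.

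- For six qualitative tests, worsening within a category does not appear and new abnormalities are not graded. On the three assumed graded scales, 6 of 10, 4 of 10 or 3 of 6 possible worsenings are hidden. This assumes that ordered grades are reported; with a plain negative/positive result nothing is hidden.
- For seven of eight variables the formulation split is left unstated, out of line with Protocol 13.1.4 and with the neighbouring SAP sections. This is a wording gap and does not prevent attribution.
- pH lacks the continuous summaries and case plots that the protocol asks for, provided it is reported numerically. The documents do not say whether it is.

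Few of the 14 planned healthy subjects are likely to be affected. Urinalysis plays no part in the bioequivalence criteria, so that conclusion is untouched.

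**What to change.** In SAP 7.11.2.2:

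1. For glucose, protein, occult blood, ketone body, bilirubin and urobilinogen, use the grades as reported by the laboratory as the shift-table categories (negative and positive if those are the only levels reported).
2. State that output (3) is provided by formulation for every variable.
3. Give pH outputs (1) to (3) by formulation, as for specific gravity.

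The cost is a change of wording in one section and some extra table rows. The tests are already scheduled, so no new sampling is needed. The downside is wider shift tables with sparse cells at this sample size. Items 2 and 3 bring the section into line with Protocol 13.1.4, item 3 on the condition that pH is numeric; item 1 goes beyond what the protocol requires.
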